1.2 Tenalisib (RP6530)

Tenalisib is a highly specific and orally available dual PI3K δ/γ and SIK-3 inhibitor with nano-molar inhibitory potency and several fold selectivity over α and β PI3K isoforms. The specificity of tenalisib towards PI3K δ and γ is evidenced by >1000 and >100-fold selectivity over α and β isoforms in an enzyme-based assay. Chemically, tenalisib is an isoflavone substituted adenine.

CONFIDENTIAL Page 18 of 66

1.3 Pre-clinical Studies with RP6530

Tenalisib has equimolar potency against both PI3K δ/γ isoforms in enzyme, cell, and blood-based assays. Additionally, the compound inhibited antigen-induced superoxide or cytokine release from primary human neutrophils or monocytes at nano-molar concentration indicating the potential in modulation of the tumour microenvironment. Studies using immortalized B and T lymphoma cell lines demonstrated the antiproliferative effect of tenalisib coupled with induction of apoptosis and a concomitant inhibition of the downstream biomarker, pAKT. Similarly, cytokine induced pAKT was inhibited in malignant primary CTCL cells isolated from patient donors. [14]

In case of solid tumours, in MC38 syngeneic murine colon carcinoma model in immunocompetent C57BL/6 female mice, treatment with tenalisib showed tumour growth inhibition (TGI) of 29% as compared to control. The combination of tenalisib and anti-PD1 reduced a mean tumour volume by 63% as compared to control.

Combination of tenalisib and IN0385 (the major metabolite of tenalisib) potentiated the activity of taxol and doxorubicin in attenuating the growth of breast cancer cell lines. In another study, IN0385 demonstrated its activity as a single agent and in combination with a PARP inhibitor, talazoparib in ovarian cancer cell lines. Addition of IN0385 potentiated the activity of talazoparib. Similarly, IN0385 demonstrated its activity in combination with olaparib in breast cancer cell lines. IN0385 also potentiated the TNF- α mediated inhibition and apoptosis in breast cancer, AML and pancreatic cancer cell lines, and combination of TNF- α and IN0385 resulted in GI₅₀ shift of IN0385 to left and significant inhibition of cell proliferation. Refer to the Investigator's Brochure (IB) for detailed background information on tenalisib. [14]

1.4 Clinical Experience

As of 20th April 2021, a total of 169 patients with relapsed/refractory hematological malignancies (viz. CLL, PTCL, CTCL and iNHL) have been exposed to tenalisib in either single agent or combination studies; 35 patients in RP6530-1301 study, 58 patients in RP6530-1401 study, 2 patients in RP6530+Pembrolizumab-1701 study, and 33 patients RP6530+Romidepsin-1805 study, 20 patients in RP6530-1802 study, 21 patients in RP6530-1901 study. A total of 16 patients have been rolled over to compassionate study (RP6530-1803); 4 from RP6530-1401 study, 5 from RP6530+Romidepsin-1805 study and 7 from RP6530-1901 study. In addition, 18 healthy volunteers were exposed to tenalisib in food effect study (RP6530-1501).

• Safety:

169 patients have received tenalisib at doses ranging from 25-1200 mg BID. Tenalisib is generally well tolerated in patients with hematological malignancies (at doses ranging from 25 mg BID to 1200 mg BID) and aggressive lymphomas such as TCL (at doses ranging from 200 mg BID to 800 mg BID). The most frequently reported related AEs (all grades) that occurred in more than 10% of patients included alanine aminotransferase (ALT) increased, aspartate aminotransferase (AST) increased (15.6% each) and diarrhea (11.9%). The most frequently reported related Grade ≥3 AEs were ALT increased, AST increased (7.4% each) and neutropenia (4.4%). Other Grade ≥3 laboratory abnormalities included gamma-glutamyl transferase (GGT) increased, International normalized ratio (INR)

CONFIDENTIAL Page 19 of 66

increased, hyperglycemia and hypertriglyceridemia reported in one patient each. Hypophosphatemia and thrombocytopenia were reported in two patients.

Pharmacokinetics:

In RP6530-1301 study, pharmacokinetics (PK) was evaluated in patients with hematological malignancies at doses ranging from 25-1200 mg BID and in TCL at doses ranging from 200 to 800 mg BID. Maximum systemic exposures assessed by AUC_{0-t} as determined on Cycle 1 Day 1 (C1D1) were found at these doses. Tenalisib showed rapid absorption (between 0.5 and 2 h), with C_{max} and AUC_{0-t} increasing proportionately with dose on C1D1. There was no significant accumulation between C1D1 and C2D1. Trough concentrations did not show any specific trends from one day to the other even though concentrations increased generally with doses. $T_{1/2}$ were similar for all dose levels.

Clinically relevant concentrations of IN0385, a major metabolite of tenalisib, were observed in patients treated with tenalisib. Exposures (C_{max}) for IN0385 ranged between 1.2 to 2.2 times of tenalisib (the parent compound). Elimination kinetics of IN0385 were however similar to tenalisib with half-life ranging between 2 - 4.5 hours.

• Efficacy:

In Phase I study (RP6530-1301 study) in hematological malignancies, two patients (6.5 %) showed CR and 4 patients (12.9%) showed PR in 31 efficacy evaluable patients. The ORR was 19.4 % with a DCR of 61.3%. Duration of response was 5.68 (1.5-15.7) months. The time to onset of response was 3.49 months (1.4-11.9 months). PFS was 4.62 months (1.0-17.5 months).

In patients with TCL (RP6530-1401 study), a total of 16 out of 35 evaluable patients responded to tenalisib with ORR of 45.7% and a median DOR being 4.37 months. The best response of CR was noted in a total three (8.6%) patients while PR was noted in 13 (37.1%) patients. The ORR among CTCL and PTCL patients were similar and were 45.0% and 46.7% respectively. The median DOR among PTCL patients was 4.9 months whereas it was 3.83 months in CTCL patients.

In patients with indolent NHL (RP6530-1802 study), 20 patients received tenalisib in Part 1. Only one FL patient showed a PR out of 19 evaluable patients in the study. In patients with CLL (RP6530-1901 study), seven patients showed PR with ORR of 33% in 21 evaluable patients of Part I. Remaining 14 patients showed a stable disease. The median DOR was 5.23 months.

CONFIDENTIAL Page 20 of 66

1.5 Rationale

1.5.1 Study Rationale

Breast cancer is the most common cancer diagnosed in women and is the second leading cause of cancer-related deaths. It is categorized into different histopathological subtypes based on expression of estrogen receptor (ER), progesterone receptor (PR), and human epidermal growth factor receptor 2 (HER2). HR-positive, HER2-negative breast cancer is the most common subtype. Most patients with HR-positive, HER2-negative breast cancer are initially diagnosed and treated at an early stage with a combination of surgery with or without radiation and adjuvant endocrine therapy with or without adjuvant chemotherapy.

Approved therapies for patients with HR-positive, HER2-negative advanced or metastatic breast cancer include hormonal-based (aromatase inhibitor [AI], fulvestrant) therapies in combination with CDK 4/6 inhibitors (abemaciclib, palbociclib, ribociclib), everolimus with exemestane, alpelisib with fulvestrant, hormonal monotherapy (AI, fulvestrant, tamoxifen), and chemotherapy (capecitabine, eribulin, ixabepilone, paclitaxel protein-bound, gemcitabine, etc.). [15] Metastatic breast cancer is incurable and has a 5-year survival rate of approximately 25%. Treatment options for all patients remain an area of significant unmet need.

The PI3K pathway is a central oncogenic pathway that regulates cell proliferation, cell metabolism, growth, survival, and apoptosis. Constitutive activation of PI3K down signaling is a critical step in mediating the transforming potential of oncogenes and tumour suppressors in many tumour types. Constitutive activation of the PI3K pathway has also been linked to resistance for a variety of therapeutic interventions, including chemotherapy, hormonal therapy, and anti-HER2 therapies. Similarly, activation of the PI3K pathway has been linked to *de novo* or acquired resistance to endocrine therapy, chemotherapy, and radiotherapy. Targeting PI3K pathway is therefore a potential therapeutic strategy for breast cancer.

Furthermore, in some solid tumours p110 δ is shown to dampen the activity of PTEN tumour suppressor. Given that PTEN somatic mutations occur in a small percentage of human breast cancers and that p110 δ is highly expressed in this tumour type, PI3K δ inhibitors may provide an excellent opportunity in the intervention of breast cancer. PI3K γ plays major role in immunosuppressive microenvironment. PI3K γ inhibitors plays major role modulation tumour micro-environment leading to inhibition of tumour growth and metastasis.

Overexpression of SIK is found in specific types of cancer such as ovarian and breast cancers. SIK3 is highly expressed in around 55% breast cancer patients. Elevated SIK3 expressions in breast cancer cells are shown to contribute to tumourigenesis. Mechanistic studies have demonstrated that SIK3 played a crucial role in induction of G1/S-phase release of cell cycle, along with enhanced expression of metastasis specific chemokine CXCR4 in breast cancer cells. The phosphorylation of HDAC4, a well-documented downstream target of SIK3, is known to induce cell proliferation and malignancy. [16] Also, high expression of SIK3 stimulates mTOR-mediated aerobic glycolysis and cell proliferation of breast cancer cells. [17]

CONFIDENTIAL Page 21 of 66

These evidences suggest the role of PI3K and SIK in oncogenesis and its maintenance and hence its inhibition can potentially lead to inhibition of growth of locally advanced or metastatic breast cancers. Several PI3K inhibitors, most of which are orally administered, either with broad activity against all PI3K isoforms or selectivity for specific isoforms, are in clinical development (**Table 1**).

Tenalisib is a highly selective PI3K δ/γ and SIK3 inhibitor with a differentiated safety profile. In addition to PI3K class effects, anti-tumour activity of tenalisib is through three distinct and non-overlapping mechanisms; a) inhibition of δ isoform enhances an anti-tumour cytotoxic T-cell response by reducing the immune-suppressive function of regulatory T cells (Tregs), b) inhibition of γ isoform decreases tumour growth by modulating tumour micro-environment, c) Inhibition of SIK3 potentiates the activity of TNF- α and thus increases apoptosis.

Tenalisib has been evaluated in >150 patients with haematological malignancies and demonstrated encouraging activity in indications such as T-cell lymphoma (TCL) and Hodgkin's Lymphoma (HL). The added influence of SIK-3, which is relevant to solid tumours, could potentially augment the activity of tenalisib in aggressive tumours.

Tenalisib demonstrated pre-clinical activity as a single agent and in combination in multiple cell lines and syngeneic model representative of various solid tumours. In MC38 syngeneic murine colon carcinoma model in immunocompetent C57BL/6 female mice, treatment with tenalisib reduced a mean tumour volume with TGI of 29% as compared to control. The combination of tenalisib and anti-PD1 reduced a mean tumour volume with TGI of 63% as compared to control, possibly indicating modulation of tumour microenvironment through inhibition of γ isoform by tenalisib.^[14]

Combination of tenalisib and IN0385 potentiated the activity of taxol and doxorubicin in attenuating the growth of breast cancer cell lines. In another study, IN0385 demonstrated its activity as a single agent and also in combination with talazoparib in ovarian cancer cell lines. Addition of IN0385 at 5μ M potentiated the activity of talazoparib. Similarly, IN0385 demonstrated its activity in combination with olaparib in breast cancer cell lines. Addition of IN0385 potentiated the TNF- α mediated inhibition and apoptosis in breast cancer, AML and pancreatic cancer cell lines, and combination of TNF- α and IN0385 resulted in GI₅₀ shift of IN0385 to left and significant inhibition of cell proliferation. [14]

Based on these pre-clinical evidences with tenalisib and clinical evidences from other PI3K inhibitors, it is proposed that tenalisib has the potential to treat the patients with locally advanced and metastatic breast cancer.

1.5.2 Rationale for Dose Selection

The safety and tolerability of tenalisib has been established up to doses of 1200 mg BID (total daily dose of 2400 mg) in patients with relapsed/refractory hematologic malignancies. No dose limiting toxicity was seen at this dose level. The efficacy of tenalisib at 800 mg BID has been evaluated as a single agent as well as in combination in patients with TCL and showed impressive response in this patient population. [19,20]

CONFIDENTIAL Page 22 of 66

In this study of breast cancer, the objective is to evaluate two doses of tenalisib and thus identify the optimal dose amongst the two which shows signal of clinical efficacy with an acceptable safety profile. This dose can be thus taken ahead for further development. Hence doses of 800 mg BID and 1200 mg BID are proposed in this Phase II study.

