2 TRIAL OBJECTIVES

2.1 Primary Objective

 To assess the anti-tumour activity of tenalisib in patients with locally advanced or metastatic breast cancer.

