3.3 Randomization

This is a randomized, open label study. Eligible subjects will be randomized to one of the two groups (Group 1: Tenalisib 800 mg BID and Group 2: Tenalisib 1200 mg BID) in 1:1 ratio based on the central randomization list generated by a validated software.

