9.2 Determination of Sample Size

A sample size of 20 per group will provide a precision of 13% for a two-sided 90% confidence interval based on Exact (Clopper-Pearson) method assuming the percentage of patients without progression at the end of 6 month is 20%. Thus, total 40 patients (20 patients in each group) will be enrolled in the study.

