2. INTRODUCTION

This statistical analysis plan (SAP) contains definition of analysis population(s), derived variables and statistical methods for efficacy and safety analysis.

The SAP is written based on the following documentation:

Document	Date	Version	
Protocol	29June2021	1.0	
eCRF	24Sep2021	1.0	
eCRF	16June2022	5.0	

Breast cancer is the most common cancer diagnosed in women and is the second leading cause of cancerrelated deaths. Based on these pre-clinical evidences with tenalisib and clinical evidences from other PI3K inhibitors, it is proposed that tenalisib has the potential to treat the patients with locally advanced and metastatic breast cancer.

The objective of the study is to assess the anti-tumour activity along with safety and efficacy of tenalisib at two different doses in order to identify the optimal dose that shows signal of clinical efficacy with an acceptable safety profile. This dose can be thus taken ahead for further development. Doses of 800 mg BID and 1200 mg BID are proposed in this Phase II study.

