8.7.1 Analysis of Primary Efficacy Variable

The primary endpoint will be analysed to assess the anti-tumour activity of tenalisib in patients with locally advanced or metastatic breast cancer.

The summary of patients without disease progression at the end of 6 months will be provided by frequency and percentage along with 95% confidence intervals of these percentages for both the treatment groups. The 95% confidence intervals of these percentages will be calculated using exact method based on binomial distribution.

The efficacy analysis will also be summarized by metastasis type (de novo metastasis, recurrent metastasis) and overall.

> Page 16 of 106 ST-AD-032 version 01

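### The plan says it will identify the better of two randomised doses but specifies no estimate of the difference between them; a descriptive difference with a confidence interval should be added.

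*Protocol*

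**What the plan says.** **The aim.** Protocol 1.5.2 says the two doses are evaluated to "identify the optimal dose amongst the two which shows signal of clinical efficacy with an acceptable safety profile", and adds: "This dose can be thus taken ahead for further development". SAP section 2 says the study is done "in order to identify the optimal dose that shows signal of clinical efficacy with an acceptable safety profile".

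**The listed objectives.** The primary objective in Protocol 2.1 is "To assess the anti-tumour activity of tenalisib in patients with locally advanced or metastatic breast cancer". The secondary objective is safety and tolerability, and the exploratory one concerns biomarkers. SAP section 3 lists the same three. None of them compares the doses.

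**Allocation and size.** Patients are assigned to 800 or 1200 mg BID "in 1:1 ratio based on the central randomization list generated by a validated software" (Protocol 3.3). Protocol 9.2 sizes the trial on the precision of a single group's percentage: "A sample size of 20 per group will provide a precision of 13% for a two-sided 90% confidence interval based on Exact (Clopper-Pearson) method", at an assumed rate of 20%.

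**The analysis.** Under SAP 8.7.1 the primary summary "will be provided by frequency and percentage along with 95% confidence intervals of these percentages for both the treatment groups", by the exact binomial method. The shell of Table 14.2.1.1 has columns for 800 mg, 1200 mg and Overall. ORR and CBR follow the same layout (SAP 8.7.2, Table 14.2.2.1). PFS, duration of response and duration of clinical benefit are Kaplan-Meier summaries by group and overall. SAP 5.2 records no change from the protocol's analysis.

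**The concern.** The dose-choice aim concerns a contrast between two groups, and no planned output is a contrast. Neither document specifies a risk difference, a ratio or a hazard ratio. The pooled column averages over the dose, and the metastasis-type tables split by a factor that was not randomised.

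What is at stake is how the dose choice is read. Without an estimated difference, anyone using the tables for the stated purpose must set two percentages side by side and judge the gap unaided. At 20 per group a sizeable gap arises often by chance. Two separate intervals show that each rate is imprecise, but neither is the interval for the difference.

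Pre-specification matters too. The trial is open label, and Protocol 9.4.3 allows further efficacy parameters to be assessed as data emerge. A contrast chosen then would be chosen with the results in view.

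**Working it through.** **Inputs.** From Protocol 9.2 and SAP 4.5: n = 20 per group, assumed rate 20% (4/20), two-sided 90% Clopper-Pearson interval, stated precision 13%. From SAP 8.7.1: exact 95% intervals. The 7/20 result used in step 3 is an assumption for illustration; it is not in the documents.

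**1. The plan's own figure.** The 90% Clopper-Pearson interval for 4/20 is 7.1% to 40.1%. The distance from 20% down to the lower limit is 20.0 - 7.1 = 12.9 points, which rounds to the stated 13%. The distance up is 20.1 points and the half-width is 16.5 points. The stated precision is therefore reproduced as the lower-side distance, and it describes one group only. Neither document gives a precision for the difference.

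**2. Chance gaps when the doses are equal.** Let X1 and X2 be independent Binomial(20, 0.20) counts. Then P(X1 = X2) = Σ P(k)², and for d > 0, P(|X1 - X2| = d) = 2 Σ P(k)P(k + d).

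| Gap (patients) | Gap (points) | Probability |
|---|---|---|
| 0 | 0 | 0.158 |
| 1 | 5 | 0.292 |
| 2 | 10 | 0.231 |
| 3 or more | 15 or more | 1 - (0.158 + 0.292 + 0.231) ≈ 0.320 |

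The unrounded value in the last row is 0.3195. A gap of at least 10 points has probability 0.231 + 0.320 ≈ 0.55.

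**3. What an interval for the difference would show.** The Newcombe interval combines the Wilson limits (l, u) of each rate. With D = p1 - p2:

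- lower = D - √[(p1 - l1)² + (u2 - p2)²]
- upper = D + √[(u1 - p1)² + (p2 - l2)²]

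For 7/20 against 4/20:

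- p1 = 0.35, Wilson 95% limits 0.181 to 0.567
- p2 = 0.20, Wilson 95% limits 0.081 to 0.416
- D = 0.15
- lower = 0.15 - √(0.169² + 0.216²) = 0.15 - 0.274 = -0.124
- upper = 0.15 + √(0.217² + 0.119²) = 0.15 + 0.248 = 0.398

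The difference is 15 points with a 95% interval of -12 to +40 points. With 4/20 in both groups, D = 0 and the interval is about -25 to +25 points.

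**4. What the planned tables would show for the same data.** The exact 95% intervals are 15.4% to 59.2% for 7/20 and 5.7% to 43.7% for 4/20. They overlap heavily, but -12 to +40 cannot be read off them.

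**The case against.** The strongest reply is that the design is coherent as written. The listed objectives describe activity, safety and biomarkers. The sample size rests on per-group precision, and per-group exact intervals match that. The dose-choice wording sits in a rationale and an introduction, and it describes a joint judgement of efficacy and safety that an interval of -12 to +40 points cannot settle. The tables print counts and denominators, so a reader could compute the difference.

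Much of this stands. It limits the point to a cheap addition and rules out any claim that the trial misses its formal objective. It does not remove the gap. Both documents give dose identification as what the study is for, and a difference with its interval is the direct summary of the efficacy side of that question. Leaving readers to compute it also leaves the direction and method open.

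A reader might infer more than the documents support:

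- *That the SAP offers bare percentages only.* It also gives exact intervals, Kaplan-Meier quartiles with intervals and curves, and waterfall and visit-wise plots.
- *That randomisation was chosen in order to compare the doses.* Protocol 3.3 gives no reason for it.
- *That adverse-event rates need an interval for the difference too.* Protocol 9.4.2 rules out inferential safety analyses, and SAP 8.8.2 rules out inference between treatments on adverse events.
- *That the difference should be stratified by receptor subtype.* SAP 7.2 declares covariate adjustment not applicable, randomisation is not described as stratified, and 20 patients per group over the three subtypes in Table 14.1.3.1 would leave strata too thin.

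A further caution is sound. The Table 14.2.1.1 footnote summarises patients by treatment duration of at least 180 days. A difference built on that count would partly measure time on drug.

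**Conclusion.** The point holds as a modest, low-cost improvement. Protocol 1.5.2 and SAP section 2 state a dose-choice aim, and no planned output estimates the difference between doses. With 20 per group and equal true rates of 20%, a gap of 15 points or more appears in about 32% of trials. An illustrative 15-point gap carries a 95% interval of about -12 to +40 points.

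These figures assume independent patients, a full 20 per group in the analysis set and the protocol's 20% rate. They would change somewhat with other rates or numbers.

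The finding does not show that the trial is underpowered for a promised comparison. No between-dose hypothesis, effect size or alpha is stated, and a small phase II study need not test one. Nor does it show that the per-group analyses are wrong.

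**What to change.** In SAP 8.7.1 and 8.7.2, and in Tables 14.2.1.1 and 14.2.2.1, add a column with the 1200 minus 800 mg BID difference and its Newcombe 95% confidence interval for the 6-month percentage without progression, ORR and CBR. Label it descriptive estimation only, with no test and no selection rule. Record it in SAP 5.2 as an addition to the protocol's analysis.

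Compute the 6-month difference on progression status at 180 days over all patients in the group, as SAP 6.4.1 defines it, and reconcile the Table 14.2.1.1 footnote on treatment duration with that definition.

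Leave adverse events without an interval for the difference, and do not stratify by receptor subtype.

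The cost is one column in each table, a few lines of SAP text and the footnote correction; no extra patients, data or alpha are needed. The downside is that a wide interval is shown openly.
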